## 4. Objectives and Endpoints

### 4.1. Objectives

#### 4.1.1. Primary Objective and Endpoint

The primary objective of this study is to quantify the incidence of RC markers in high risk postsurgical patients, using a system comprised of two continuous monitoring devices, connected to a remote monitoring platform.

The occurrence of at least one of the following RC markers will be considered as primary endpoint for patients monitored by Capnostream 20p during both study Phases:

1. SpO2 ≤ 90% for ≥ 3 minutes.
2. RR ≤ 8 or ≥ 22 bpm for ≥ 3 minutes.
3. etCO2 ≤ 15 or ≥ 60 mmHg for ≥ 3 minutes.
4. Apnea episode lasting > 30 seconds.

The occurrence of at least one of the following RC markers will be considered as primary endpoint for patients monitored by PM1000N-RR during both study Phases:

1. SpO2 ≤ 90% for ≥ 3 minutes.
2. RR ≤ 8 or ≥ 22 bpm for ≥ 3 minutes.

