## 10. Adverse Events and Device Deficiencies

In this study the following AEs will be collected:

- All AEs with an underlying respiratory cause
- All SAEs
- All adverse device effects (ADE)

In addition, device deficiencies (DD) will be collected for this study.

RC markers will not be considered AE if the patient is asymptomatic and no actions are taken.

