### 4. Study Objectives

#### 4.1. Primary Objective

The primary objective of this study is to quantify the incidence of RC markers in high risk postsurgical patients, using a system comprised of two continuous monitoring devices, connected to a remote monitoring platform.

The occurrence of at least one of the following RC markers will be considered as primary endpoint for patients monitored by Capnostream 20p during both study Phases:

- SpO2 ≤ 90% for ≥ 3 minutes (or SpO2 ≤ 90% for < 3 min with an action taken);
- RR ≤ 8 or ≥ 22 bpm for ≥ 3 minutes (or RR ≤ 8 or ≥ 22 bpm for < 3 min with an action taken);
- EtCO2 ≤ 15 or ≥ 60 mmHg for ≥ 3 minutes (or etCO2 ≤ 15 or ≥ 60 mmHg for < 3 min with an action taken);
- Apnea episode lasting > 30 seconds.

The occurrence of at least one of the following RC markers will be considered as primary endpoint for patients monitored by PM1000N during both study Phases:

- SpO2 ≤ 90% for ≥ 3 minutes (or SpO2 ≤ 90% for < 3 min with an action taken);

- RR  $\leq$  8 or  $\geq$  22 bpm for  $\geq$  3 minutes (or RR  $\leq$  8 or  $\geq$  22 bpm for < 3 min with an action taken).

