## 7.9. Evaluation of Objectives

### 7.9.1. Primary Endpoint

The Primary Endpoint of the Study is to quantify the incidence of RC markers in high risk postsurgical patients, using a system comprised of two continuous monitoring devices, connected to a remote monitoring platform. The proportion and rate of “At least one RC marker” event will be calculated and reported.

The “At least one RC marker” event is defined as the occurrence of at least one of the following RC markers:

1.  $\text{SpO}_2 \leq 90\%$  for  $\geq 3$  minutes (or  $\text{SpO}_2 \leq 90\%$  for  $< 3$  min with an action taken);
2.  $\text{RR} \leq 8$  or  $\geq 22$  bpm for  $\geq 3$  minutes (or  $\text{RR} \leq 8$  or  $\geq 22$  bpm for  $< 3$  min with an action taken);
3.  $\text{EtCO}_2 \leq 15$  or  $\geq 60$  mmHg for  $\geq 3$  minutes (or  $\text{EtCO}_2 \leq 15$  or  $\geq 60$  mmHg for  $< 3$  min with an action taken);
4. Apnea episode lasting  $> 30$  seconds.

For patients monitored by PM1000N, only RC markers #1 and #2 will be considered.

RC determination will be assessed by a physician belonging to the “other” site (cross assessment by the sites). This assessment will be made by the analysis of both device and clinical data for each patient. For each patient all potential RC episodes will be derived using the Detection Tool (see Section 10.1) and will be submitted to the other site’s physician in order to adjudicate the potential RC episodes starting from episodes most likely to be RC. The adjudication will stop at the first RC occurring per patient.

The Events’ rates will be computed as (total number of “At least one RC marker” event)/(total number of time-person in PPS) and will be reported separately for each arm and phase of the study. Events’ rates will be displayed together with their 95% confidence interval (95%CI).

If the number of episode per patient result unbalanced, adjusted rates will be reported using the GEE model, together with their 95% confidence interval (95%CI).

If appropriate, also the events’ rates for each RC marker will be reported separately, for each arm and phase of the study.

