### 7.9.2. Secondary Endpoints

The secondary endpoints are:

1. To compare phases in terms of Primary endpoint incidence;
2. To compare phases in terms of respiratory and SAE incidence, number of ICU transfers and related length of stay, Code blues and RRT responses.
3. To evaluate the rate of clinical early interventions performed by nurse staff to prevent a potential AE, introducing continuous monitoring devices connected to a remote monitoring platform;
4. To evaluate the nurses’ satisfaction related to the monitoring system introducing continuous monitoring devices connected to a remote monitoring platform;
5. To establish the Predictive values of  $\text{EtCO}_2$ , RR,  $\text{SpO}_2$ , plethysmography-derived RR, IPI and EWS in respect to respiratory and other SAE.

In order to evaluate secondary **endpoints #1 and #2**, the incidence of events will be reported together with the comparison between phases, by means of the Chi-square test or Fisher exact test for extreme

proportions, as appropriate. If the monitoring/study exposure results different between phases, also the rates of events will be reported, together with the 95% Poisson Confidence Intervals. The Poisson regression model will be used to calculate the Incidence Rate ratio (IRR), with the d-scale option.

For **endpoint #3**, the rate of clinical early interventions will be calculated as (number of early interventions)/(total time-person in FAS) and it will be reported together with the 95% Poisson Confidence Interval.

Early interventions include, as defined in CRF (Monitoring Period):

1. Stimulated subject to breathe;
2. Repositioned/opened airway;
3. Held or reduced Respiratory Depressive (RD);
4. Added or increased supplemental oxygen;
5. Ventilation support;
6. Other

**Endpoint #4** will be evaluated reporting a summary of the nurses' satisfaction answers.

To identify the predictive values for EtCO2, RR, SpO2, plethysmography-derived RR, IPI and EWS, which can predict respiratory and other SAE, a sensitivity analysis will be performed (**endpoint #5**), and the following parameters will be reported, for each RC marker:

1. **Sensitivity** = 
$$\frac{(\# \text{ of clinical events "Yes" and with RC marker "Yes"})}{(\# \text{ of clinical events "Yes"})} = \frac{TP}{(TP+FN)}$$
2. **PPV** = 
$$\frac{(\# \text{ of clinical events "Yes" and with RC marker "Yes"})}{(\# \text{ of events with RC marker "Yes"})} = \frac{TP}{(TP+FP)}$$

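### SAP endpoint #5 is at risk of incorporation bias: staff action helps define the SpO2, RR and EtCO2 markers and also bears on the adverse events they should predict

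*SAP*

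**What the plan says.** **Index test.** Endpoint #5 concerns EtCO2, RR, SpO2, plethysmography-derived RR, IPI and EWS, "which can predict respiratory and other SAE, a sensitivity analysis will be performed" (SAP 7.9.2). The results are tied to markers: "the following parameters will be reported, for each RC marker" (SAP 7.9.2). The SAP gives formulas for sensitivity and PPV and drops specificity and NPV because true negatives cannot be identified.

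**Marker definition.** For RR, Protocol 4.1.1 uses duration only: "RR ≤ 8 or ≥ 22 bpm for ≥ 3 minutes". SAP 4.1 and 7.9.1 add a second route: "or RR ≤ 8 or ≥ 22 bpm for < 3 min with an action taken". SpO2 and EtCO2 have the same addition. Apnea does not: "Apnea episode lasting > 30 seconds".

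**Reference standard.** The Protocol names respiratory AEs and SAEs; the SAP wording is respiratory and other SAE. Protocol section 10 states: "RC markers will not be considered AE if the patient is asymptomatic and no actions are taken". Appendix A gives a similar exclusion but refers only to invasive actions. Several anticipated respiratory events in Table 5 of Appendix A are described by the support they require.

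**Window.** The time window linking markers to events is still to be defined. The SAP's example is one minute on either side of the event.

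**The concern.** A predictive value is informative when the test result is obtained without knowledge of the outcome, or of the response to it. Here part of the test result is whether staff intervened. Intervention also bears on whether a respiratory AE is recorded, and for some anticipated events the support given is part of the description. A brief excursion beside a treated event can count as a hit because it was treated. An identical excursion elsewhere, with no response, is neither a hit nor a false alarm because it is not a marker.

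The stated aim is to characterise what the monitored parameters predict. A monitor cannot observe whether a nurse will act. Sensitivity computed on the SAP marker would therefore mix signal performance with staff behaviour, and readers could take it as a property of the device.

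**Working it through.** The documents give no expected sensitivity, PPV or event count for endpoint #5, so there is no planned figure to reproduce. All numerical inputs below are assumptions; the structure comes from SAP 4.1, 7.9.1 and 7.9.2 and Protocol 4.1.1.

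**1. Sensitivity.** Every Protocol marker is also an SAP marker, and the SAP adds short excursions with an action. With events and window held fixed, let s0 be sensitivity with the duration-only marker and *a* the share of the remaining events that have a short, acted-on excursion in the window. Then

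sensitivity = s0 + a(1 − s0).

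| s0 | a = 0.10 | a = 0.25 | a = 0.50 |
|---|---|---|---|
| 0.20 | 0.28 | 0.40 | 0.60 |
| 0.60 | 0.64 | 0.70 | 0.80 |

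It cannot fall, because a(1 − s0) is never negative.

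**2. PPV.** Let M0 be the markers of at least 3 minutes, PPV0 their PPV, Ma the added short markers, and *g* the share of added markers paired with an event. Then

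PPV = (M0·PPV0 + Ma·g)/(M0 + Ma).

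With M0 = Ma = 100 and PPV0 = 0.10, this is (10 + 100g)/200: 0.05 at g = 0, 0.10 at g = 0.10, 0.15 at g = 0.20 and 0.55 at g = 1. PPV rises only if g exceeds PPV0.

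**3. The same point in counts.** Assume 20 events; 20 episodes of at least 3 minutes, 5 of them at events; and 200 shorter excursions, of which 10 are at events and acted on, 20 are elsewhere and acted on, and 170 are not acted on.

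- Duration-only marker: sensitivity 5/20 = 25%, PPV 5/20 = 25%.
- SAP marker: sensitivity 15/20 = 75%, PPV 15/(20 + 30) = 30%.
- SAP marker with 30 acted-on excursions elsewhere instead of 20: PPV 15/60 = 25%.
- SAP marker with 40 elsewhere: PPV 15/70 = 21.4%, below the duration-only figure.
- Device rule counting excursions of any length: sensitivity 15/20 = 75%, PPV 15/220 = 6.8%.

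The last line shows what the clause does in this example. It keeps the hits of the any-duration rule but removes the 170 excursions to which nobody responded.

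**4. Phase.** In Phase I alarms are silenced and screens blinded (Protocol section 5). In Phase II the recommended alarms use the same cut-offs as the markers but sound after 30 seconds (Appendix B). That leaves 180 − 30 = 150 seconds in which a response to an alarm can turn a short excursion into an SAP marker. Sites may change the settings, so the size of this difference is not known.

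**5. Window.** A symmetric window accepts excursions, and actions, that follow the event. Those are consequences or coincidences, not predictions. This also affects apnea, which has no action clause.

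**The case against.** Five arguments limit the point.

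- **The clause has a rationale.** In Phase II a nurse may end an excursion before 3 minutes, and a duration-only marker would miss it. This stands, and is why the action-inclusive result deserves a place as a supplement. It does not make that result a measure of the signal.
- **The AE rules are exclusions.** Section 10 and Appendix A say when a marker is not an AE; neither says that an action creates one. The SAP describes early interventions as preventing a potential AE, so the two are distinct. SAEs such as death do not turn on a brief nursing action. All of this stands. A reader might infer that marker and event are circular by definition, but the text supports only partial dependence.
- **PPV.** A reader might infer that PPV is inflated too. It is not so by construction: stimulation, repositioning or added oxygen can create markers that never pair with an event, and these lower PPV.
- **Adjudication.** For the primary endpoint, SAP 7.9.1 says of RC determination: "This assessment will be made by the analysis of both device and clinical data for each patient". A reader might infer that endpoint #5 rests on assessors who know the outcome. The SAP does not say that adjudicated RCs are used there. Adjudication also stops at the first RC per patient, so it could not supply marker status for every event, and Protocol 8.10 makes device memory the source for marker number and duration. The input to endpoint #5 is simply unstated.
- **PPV formula.** Its numerator counts clinical events and its denominator counts events with a positive marker. The unit is ambiguous, but the formula is not shown to be wrong.

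**Conclusion.** The concern holds as a risk of incorporation bias for the SpO2, RR and EtCO2 markers. It rests on two textual facts: the SAP marker contains an action clause that the Protocol marker lacks, and action or required support also bears on respiratory AE status. Against the duration-only marker, with events and window fixed, sensitivity stays equal or rises; under the assumed inputs 0.20 becomes 0.28 to 0.60, and 0.60 becomes 0.64 to 0.80. The effect on PPV can go either way. The true size cannot be derived from the documents and may differ by phase. The symmetric example window is a separate weakness in the same analysis.

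The action argument does not reach apnea, nor IPI and EWS, for which the SAP defines no marker. The stronger conclusion that the whole endpoint is circular, with both measures inflated, is not supported. The primary analysis is not at issue here; this is a descriptive secondary endpoint in a pilot study, but one whose figures could be read as device performance.

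**What to change.** In SAP 7.9.2, endpoint #5:

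1. Use as index test the unadjudicated Detection Tool episodes at the Protocol 4.1.1 thresholds and durations, without the action clause. Show the action-inclusive SAP marker only as a supplementary result, noting that action can cut an excursion short in Phase II.
2. Replace the symmetric example with a pre-specified pre-event window, and count only markers that start before event onset. Protocol 10.2 already requires the date and time of each AE.
3. Count sensitivity per clinical event and PPV per aggregated marker episode, with intervals that account for clustering within patients.
4. Report the results by phase.
5. Reconcile Protocol section 10 with Appendix A on which actions bear on AE status.

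Excluding AEs judged to exist only because a marker was acted on is not advisable, since that judgement would itself use knowledge of the marker.

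The cost is SAP rewording, the reconciliation of two Protocol statements, and a Detection Tool run at the Protocol durations. No new data are needed. The reported sensitivity may be less favourable.

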#### 4.1.2. Secondary Objectives and Endpoints

The study secondary objectives are the followings:

1. To compare the two study Phases (see Section 5) in terms of primary endpoint incidence.
2. To compare the two study Phases in terms of respiratory AEs and SAE incidence, number of ICU transfers and related length of stay, Code blues and RRT responses.
3. To evaluate the impact of introducing continuous monitoring devices connected to a remote monitoring platform on the clinical workflow, defined as the rate of clinical early interventions performed by nursing staff to prevent a potential AE (e.g. patient stimulation, Jaw thrust maneuver, oxygen administration started or increased, medication change, etc.).

4. To evaluate the impact of introducing continuous monitoring devices connected to a remote monitoring platform on clinical staff workflow, defined as clinical staffs' satisfaction related to the monitoring system.
5. To characterize the predictive values of etCO2, RR, SpO2, plethysmography-derived RR, IPI and EWS in respect to respiratory AEs and other SAE.

Related secondary endpoints are:

1. Incidence of RC markers recorded by the monitoring system during each Phase.
2. Incidence of respiratory AEs and SAE, number of ICU transfers and related length of stay, Code blues and RRT responses recorded in the two study Phases.
3. Average rate of early interventions for patient will be calculated in both study Phases. In Phase I there should only be non-alarm-triggered interventions, as in clinical practice, while in Phase II there should be two sub-groups of clinical early interventions: alarm-triggered and non-alarm-triggered.
4. Clinical staff's satisfaction related to the monitoring system's introduction in their current workflow will be evaluated through a survey performed at the end of the study.
5. Sensitivity and specificity of each monitored parameter in predicting and identifying respiratory AEs and SAE will be calculated. EWS will be the only parameter not automatically collected by the monitoring system but manually collected.

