## 12. Statistical Design and Methods

### 12.1 Sample size justification

The sample size calculation is based on primary endpoint and it was estimated using data from previous studies with a precision-based calculation. Recent data on post-surgical patient have shown a proportion of patient with the RC markers for the SpO2 ≤ 85% for ≥ 3 minutes at 13% and for RR ≤ 8 or ≥ 22 bpm

for  $\geq 3$  minutes at 1.4% in patients undergoing opioid therapy. Using this information, a minimum proportion of 10% of patients with RC markers with a sample size of 260 patients will be able to obtain a 95% confidence level with a precision of 5% (ranging from 5% to 10%) and a power of at least 0.80 defined as the probability of achieving the desired precision. Considering a 10% withdrawal or potential dropouts and a potential attrition rate to monitoring compliance of 5% a total of approximately 210 patients will be enrolled. This cohort will be used prospectively for the blinded and not blinded phase with a ratio 1:2 respectively to minimize not blinded monitored patients. The blinded phase will enroll 70 patients randomly allocated 1:1 in the Capnostream 20p and PM1000N-RR arm while the not blinded phase will enroll 140 patients with same randomized schedule.

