## 6. Determination of Sample Size

The sample size calculation is based on primary endpoint and it was estimated using data from previous studies with a precision-based calculation. Recent data on post-surgical patient have shown a proportion of patient with the RC markers for the  $\text{SpO}_2 \leq 85\%$  for  $\geq 3$  minutes at 13% and for  $\text{RR} \leq 8$  or  $\geq 22$  bpm for  $\geq 3$  minutes at 1.4% in patients undergoing opioid therapy. Using this information, a minimum proportion of 10% of patients with RC markers with a sample size of 182 subjects will be able to obtain a 95% confidence level with a precision of 5% (ranging from 5% to 10%) and a power of at least 0.80 defined as the probability of achieving the desired precision. Considering a 10% withdrawal or potential dropouts and a potential attrition rate to monitoring compliance of 5% a total of approximately 210 subjects will be enrolled. This cohort will be used prospectively for the blinded and not blinded phase with a ratio 1:2 respectively to minimize not blinded monitored subjects. The blinded phase will enroll

70 subjects randomly allocated 1:1 in the Capnostream 20p and PM1000N arms while the not blinded phase will enroll 140 subjects with same randomized schedule.

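### Endpoint #5 judges SpO2, RR and etCO2 only at one fixed yes/no cut each and reports no false-positive rate; a full-scale analysis should be added beside the planned table

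*SAP*

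**What the plan says.** Protocol 4.1.2 sets the endpoint: "Sensitivity and specificity of each monitored parameter in predicting and identifying respiratory AEs and SAE will be calculated". SAP 4.2 repeats the promise of sensitivity and specificity. The parameters are etCO2, RR, SpO2, plethysmography-derived RR, IPI and EWS.

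SAP 7.9.2 then specifies a two-by-two table of RC marker yes/no against clinical event yes/no, "and the following parameters will be reported, for each RC marker". Only sensitivity and PPV are defined, both as counts of events. The section states that true negatives cannot be identified, so specificity and NPV are not calculated. The time window linking marker to event is left open, with one minute either side as an example.

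The markers come from the primary endpoint (SAP 4.1 and 7.9.1). An SpO2, RR or etCO2 limit must be crossed for at least 3 minutes, or for less if staff acted. Low and high RR form one marker, as do low and high etCO2. IPI and EWS have no marker.

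The SAP gives no ROC analysis, alternative cut or continuous model for this endpoint. The protocol synopsis mentions logistic regression for all secondary outcomes, and Protocol 12.3 for one that it does not name.

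The only RR frequency is in SAP 6: "minutes at 1.4% 4 in patients undergoing opioid therapy". The same section gives 13% for SpO2 at a stricter limit of 85%.

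**The concern.** Sensitivity depends on where the cut lies as well as on how well the parameter discriminates. Loosening a cut raises sensitivity and false positives together. Without specificity, a reader of the planned table cannot tell which of the two explains a high or low figure. The cuts may have very different positivity rates: SAP 6 itself cites 1.4% and 13% for two of them, at its own limits. Protocol 5.2 also says that the study will allow the two devices to be evaluated on sensitivity, which invites exactly this reading.

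Two further losses follow. Merging low and high RR (or etCO2) hides which direction carries the signal. A table built on RC markers also cannot cover IPI or EWS, which the endpoint names. At stake is whether the pilot can say anything usable about which signals precede clinical events, from recordings that are already stored.

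**Working it through.** **Inputs from the documents.** Evaluable N: "a minimum proportion of 10% of patients with RC markers with a sample size of 182 subjects" (SAP 6). RR marker frequency: 1.4% (SAP 6). Allocation 1:1 by device (SAP 5.3), so about 182/2 = 91 evaluable per device. Capnographic RR, etCO2 and IPI exist only in the Capnostream arm and plethysmographic RR only in the PM1000N-RR arm (Protocol 5). SpO2 is measured in both.

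**The plan's own figure.** The smallest n for which an exact 95% interval has half-width of at most 5 points with probability at least 0.80, at a true 10%, is 179. At 182 that probability is 0.855. Inflation: 182 × 1.15 = 209.3, so 210. The SAP's 182 is therefore consistent with 210 enrolled. The 260 in Protocol 12.1 is not (260 × 1.15 = 299), so 182 is used here.

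**Step 1: same discrimination, different cuts.** Assume a binormal model with AUC 0.70. The mean shift is d = √2 × Φ⁻¹(0.70) = 1.414 × 0.524 = 0.742, and sensitivity at false-positive rate f is Φ(d − z), with z the 1 − f normal quantile. The two planning frequencies stand in for f (an assumption).
- f = 1.4%: Φ(0.742 − 2.197) = 7%.
- f = 13%: Φ(0.742 − 1.126) = 35%.

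Two equally good parameters would thus show a fivefold difference in sensitivity.

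**Step 2: expected RR-marker patients if the 1.4% applied.**
- Both devices: 182 × 0.014 = 2.5 (95% binomial range 0 to 6).
- Per device: 91 × 0.014 = 1.3 (0 to 4), with a chance of none of 0.986^91 = 28%.
- With 3 positives, the exact 95% CI for PPV is 1% to 91% at 1/3 and 29% to 100% at 3/3.
- If the frequency were 5% or 10% instead (assumptions): 91 × 0.05 = 4.6 or 91 × 0.10 = 9.1 per device.

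**Step 3: information lost by the cut.** Simulated power to separate event from event-free patients: AUC 0.70, two-sided 0.05, Mann-Whitney on the full scale against Fisher's exact test on the yes/no marker, with positivity in event-free patients of 1.4% to 37%. The documents give no event numbers, so these are assumed.

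| Patients | Events | Full scale | Yes/no marker |
|---|---|---|---|
| 91 (one arm) | 5 | 31% to 33% | 5% to 21% |
| 91 (one arm) | 10 | 56% | 13% to 41% |
| 182 (SpO2 only) | 20 | 83% to 87% | 26% to 66% |

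The ranges include repeat simulations. The full scale is better in every row, but within one arm neither analysis is strong.

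**The case against.** **The cuts are not arbitrary.** They are the primary-endpoint limits and match the alarm settings recommended for Phase II in Protocol Appendix B. Performance at the value where staff are alerted is a legitimate target, and AUC is less direct for that. This stands, and is why the planned table should be kept.

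**No test is planned.** Endpoint #5 is descriptive, so the power figures measure information lost and are not a property of the plan. This stands. The case rests mainly on Step 1 and on the missing specificity.

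**True negatives cannot be identified.** That holds when the unit is an event in continuous recording. It does not hold at patient level, where event-free patients with an equal length of record are countable negatives.

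**Raw device values bypass cross-site adjudication.** Protocol 8.7 describes displaced sensors, talking, eating and sensor compression. This stands as a real cost. Restricting to effective time (SAP 7.1.3) reduces it but does not remove it.

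**Stronger readings that a reader might draw.**
- That RR cannot be evaluated at all. The 1.4% comes from patients on opioid therapy and is used only for sample size. This cohort is selected on POSPOM or ARISCAT. The SAP marker is also broader, because it counts shorter episodes when staff acted. Rarity would make estimates imprecise, not impossible.
- That RR sensitivity is capped at about 13% (2.5/20). This needs an assumed 20 events and patient-level counting. The SAP formula counts events, and a patient may have several episodes.
- That the plan fails an objective to rank the parameters. The documents ask to characterise or establish predictive values and do not mention ranking.
- That full-scale power would be 83% to 87% for RR. That uses 182 patients, but each RR measurement exists in about 91.

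**Conclusion.** The point holds as a limitation of the planned analysis. As written, endpoint #5 yields sensitivities at unmatched cuts with no false-positive rate, omits the specificity that both documents promise, merges opposite directions of RR and etCO2, and has no method for IPI or EWS. Differences in cut alone could move sensitivity from 7% to 35% at the same discrimination (binormal model, AUC 0.70, planning frequencies used as false-positive rates; all assumptions).

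The RR-specific concern is conditional. If the marker were as rare as 1.4%, about 1.3 patients per device would be positive and the predictive values would be uninterpretable. The documents do not show that it will be that rare.

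This is a descriptive secondary endpoint in a pilot, so the change is advisable and does not affect the primary result. A full-scale analysis makes better use of the recordings but does not cure small event numbers.

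**What to change.** In SAP 7.9.2, keep the sensitivity and PPV table at the RC-marker cut and add a patient-level analysis:

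1. Analyse each parameter within the arm or arms where it is measured.
2. For patients with a clinical event during monitoring, take the most extreme value sustained for 3 minutes of effective-time recording in a window of fixed length before the event. For event-free patients, take the same summary over an equal length of record, chosen by a rule fixed in advance. The window must be set in the SAP before the data are examined. The example of one minute either side is too short for a 3-minute summary and includes time after the event.
3. Summarise lowest SpO2, lowest RR, highest RR, lowest etCO2 and highest etCO2 separately. Include IPI and EWS on their own scales.
4. Report AUC with 95% CI, and sensitivity at one common false-positive rate, for example 10%. This fixes specificity at 90% for every parameter and so restores the promised measure.
5. Where a parameter has an RC marker, also report the proportion of event-free patients positive at that cut, so that the retained table has its specificity.

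The cost is SAP wording and programming on device memory data that the study already exports and stores. The downsides are two directional summaries each for RR and etCO2, unadjudicated values that may include artefact, and wide intervals. With 5 to 10 events among 91 patients (assumed), the report should present the AUCs as exploratory.
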